## ***Data collection***

*Objective 1: To determine the efficacy of an electronic reminder system in reducing urinary catheter usage*

Data will be collected by a specific staff member at the hospital, supported by the research team. Where data collection results in an increase in workload for the hospital staff (e.g. not part of usual practice), the research team will provide additional resources in the form of funding to account for additional hours for existing staff members or employment of new staff members for the purpose of data collection. The research team will provide the hospital staff member(s) with training about the project, data collection processes and data collection tools, as well as ongoing on-site and telephone support. For the purpose of this protocol, the dedicated hospital staff member(s) will be referred to as hospital personnel.

The figure below (Figure 2) summarises the data collection process with further details provided below.

*Figure 2.* Overview of the data collection process

Hospital personnel will prospectively collect data five days a week on participating hospital wards, during both control and intervention periods. Hospital personnel will visit inpatient areas and patients who receive an indwelling urinary catheter will be identified and followed-up until discharge or catheter removal. Hospital personnel will check that a CATH TAG has been attached to every catheter, on wards that have crossed over to the intervention. The following information will be collected: hospital number, age, sex, date of admission, date and time of catheter insertion, reason for censoring follow-up, date of discharge or catheter removal, designation of person

inserting the catheter, ward and allocation to control or intervention ward. A review of microbiology results will be undertaken by the hospital personnel for each person who receives a catheter and has a urinary sample taken. If a person has a positive urine culture after catheterisation and prior to removal, the following will be collected: data of specimen collection, organism(s) isolated, colony forming units, white cell count.

Table 3 outlines the data to be collected, data sources and timing of data collection. The number of catheter days for each patient included in the study will be estimated from the date of catheter insertion to the date of removal. Hospital personnel will record all captured data locally, on a spreadsheet designed by the research team specifically for the purpose of the trial.

Table 3. Types, sources and timing of data collection

Data collected	Source	Collected by	Timing	Used for
Details of patient who received a catheter:				

 
Hospital number
 
	Medical notes	Hospital personnel	Control and intervention periods	Link to laboratory data

 
Date of birth
 
	Medical notes	Hospital personnel	Control and intervention periods	Data analysis

 
Sex
 
	Medical notes	Hospital personnel	Control and intervention periods	Data analysis

 
Date of admission
 
	Medical notes	Hospital personnel	Control and intervention periods	Data analysis

 
Date and time of catheter insertion
 
	Medical notes	Hospital personnel	Control and intervention periods	Calculating catheter days Data analysis

 
Date and time of catheter removal
 
	Medical notes	Hospital personnel	Control and intervention periods	Calculating catheter days Data analysis

 
Reason for censoring follow-up (discharged, catheter removal, transfer from control to intervention wards or vice versa)
 
	Medical notes	Hospital personnel	Control and intervention periods	Data analysis
Additional information required:				

 
Designation of person inserting
 
	Medical notes	Hospital personnel	Control and intervention periods	Data analysis

catheter			periods	
• Ward		Hospital personnel		
• Intervention/Control Allocation		Hospital personnel		
Laboratory result of any patient who received a catheter:				
• Has a catheter urine sample been taken (Y/N)	Microbiology laboratory	Hospital personnel	Control and intervention periods	Data analysis
If catheter urine sample has been taken:				
• Date of specimen collection	Microbiology laboratory	Hospital personnel	Control and intervention periods	Data analysis
• Species isolated	Microbiology laboratory	Hospital personnel	Control and intervention periods	Defining the outcome
• Colony count and white cell count where appropriate / provided	Microbiology laboratory	Hospital personnel	Control and intervention periods	Defining the outcome

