### ***Intervention***

After four weeks, two wards will cross over to the intervention. The intervention is the use of the CATH TAG. A CATH TAG will be attached to each catheter. When the CATH TAG is attached to a catheter bag it will initially flash green for a set period of 20 hours. After 20 hours the green flashing light will cease and a red light will flash with increased rapidity for four hours, alerting nurses to review the patients indwelling catheter. After 4 hours the red fast flashing light will change back to the more slowly green flashing light, restarting the cycle until the catheter is removed. There is no option for nurses to manipulate the flashing light or amend the flashing cycle.

For patients who are transferred from a control ward to an intervention ward, a CATH TAG will be attached to their catheter upon transfer. Data collected up to the date of transfer will contribute to the control (ward) dataset. Following transfer, data will be contributed to the intervention (ward) dataset.

For patients who are transferred from an intervention ward to a control ward, the CATH TAG will be removed upon transfer. Data collected up to the date of transfer will contribute to the

intervention (ward) dataset. Following transfer, data will be contributed to the control (ward) dataset.

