### ***Outcomes measures***

There are two objectives for this study, (1) determining the effectiveness of the intervention and (2) the effect of the intervention on nurses' ability to deliver patient care. A summary of the objectives' key outcome measures is shown in Table 2.

Table 2. Key outcome measures

Objective 1
 
To determine the efficacy of an electronic reminder system in reducing urinary catheter usage.
	Primary outcome	1. Urinary catheter device utilization ratio (number of urinary catheter-days divided by the number of patient-days)
	Secondary outcome(s)	
1. The number of cases of catheter associated asymptomatic bacteriuria (CA-ASB) per 100 catheter days.
 
2. The number of urinary catheters inserted per 100 patient admissions

Objective 2
 
To determine whether the CATH TAG has an effect on nurses' ability to deliver patient care.
	Primary outcome	1. Perceptions of nurses about ease of use of the CATH TAG
	Secondary outcomes	
2. Perceptions of nurses about effectiveness of the CATH TAG
 
3. Changes in ownership or interest by patients in catheter management
 
4. Barriers to the CATH TAG working successfully in varied types of patients

Note: CA-ASB = catheter associated asymptomatic bacteriuria; CAUTI = catheter associated urinary tract infection

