- It is impracticable to obtain consent for a number of reasons:
  - Urinary catheters are inserted in a variety of settings within a hospital. It would not be possible for researchers to determine or access patients (participants) who are about to receive a catheter. Similarly, urinary catheters are inserted by clinicians (nurses and

medical doctors) at any time of the day, it is not possible for all staff involved in catheterisation to be reached.

- Obtaining consent would require researchers to have access to a higher level of patient history and personal data.
- The clinician obtains consent for the insertion of a catheter, as part of usual medical treatment/processes, following local hospital policy.
- Urinary catheters are often inserted at a time where the patient (participant) requires urgent medical or surgical attention. Obtaining consent related to this study may delay the insertion of a catheter, compromising patient (participant) harm and increasing the risk of harm to patients.
- Retrospective consent, i.e. an approach that would result in the researchers retrospectively contacting participants to seek permission to access their medical records would raise the following ethical issues:
  - There would be considerable loss of participants included in the study as there is no system in place to identify which patients had a catheter inserted while in hospital. As such, the research could not be conducted. If a system were established, it would be administrative in nature. Further it would require the researchers to have access data of potential participants so they could be contacted. These details would include data such as names and postal addresses – information the researchers are not required to have as part of the proposed study design.
  - There would be the risk of contacting patients who underwent significant harm whilst in hospitals, suffered a traumatic event or may have passed away. The process of acquiring informed consent retrospectively would potentially result in increased harm for those participants.
- There is no known or likely reason for thinking that participants would not have consented if they had been asked as there is no risk involved and no patient intervention.
- The clinician will be following local hospital policy regarding the insertion of a catheter.
- There is no variation of care, rather an addition to existing policies, unless contra-indicated.

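### Catheter-days are counted from insertion to removal with no ward bound, so days before arrival on an enrolled ward and after a move to a non-enrolled area enter a ward-level outcome that the tag cannot influence there

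*Protocol*

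**What the plan says.** The primary outcome for Objective 1 (Protocol, Outcomes measures, Table 2) is "Urinary catheter device utilization ratio (number of urinary catheter-days divided by the number of patient-days". Wards, in pairs, are randomised to cross over, and the Intervention section attaches the tag to catheters on wards that have done so.

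The only counting rule is in Data collection, Objective 1: catheter-days for each patient "will be estimated from the date of catheter insertion to the date of removal". The same section says that "patients who receive an indwelling urinary catheter will be identified and followed-up until discharge or catheter removal". Neither sentence mentions entry to or exit from the ward.

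The Intervention section has a splitting rule for one kind of transfer. For a move from a control to an intervention ward, "Data collected up to the date of transfer will contribute to the control (ward) dataset" and "Following transfer, data will be contributed to the intervention (ward) dataset"; a mirror rule covers the reverse move. Table 3 lists as an item "Reason for censoring follow-up (discharged, catheter removal, transfer from control to intervention wards or vice versa".

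On where catheters start, the Ethics section (Catheter data) states that "Urinary catheters are inserted in a variety of settings within a hospital". The units named as potentially eligible are medical wards, surgical wards and intensive care units. At least ten wards are to be enrolled, so others may not be.

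**The concern.** Randomisation, the device and the outcome all belong to the ward, but the count belongs to the patient's whole catheter episode. A patient catheterised in an area that is not enrolled brings the earlier days to the enrolled ward. A patient who leaves for a non-enrolled area with the catheter in place goes on adding days until discharge or removal.

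Two things are at stake. First, a tag that has not yet been attached cannot change pre-arrival days, so counting them pulls the observed effect towards zero. Second, if the denominator is ward patient-days, the numerator contains days with no counterpart in it.

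The data items add to the problem. Table 3 has a single ward item and no date of ward arrival, departure or transfer. On-ward days cannot be derived from the listed items, and an analysis plan written later cannot recover dates that were not collected.

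**Working it through.** **1. The protocol's own figures.** 10 wards × 6 months × 35 patients = 2100, as stated under Sample size. For power I used the Hussey-Hughes variance

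Var = Iσ²(σ² + Tτ²) / [(IU − W)σ² + (U² + ITU − TW − IV)τ²]

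with I = 10 wards, T = 6 periods, U = 30, W = 220, V = 110, proportions 0.50 and 0.40, correlation 0.1 and two-sided 0.05 (the protocol does not state the sidedness). If the correlation splits the total binomial variance, power is 78.0% to 79.7%, depending on which proportion sets the variance. If 0.1 is read as a coefficient of variation, power is 80.9%. Adding the between-ward variance on top gives 73.7% to 75.4%. The stated 81% is thus approached under some readings. The present point does not depend on it.

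**2. Which catheter time has a rule.**

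| Catheter time | Rule in the protocol |
|---|---|
| Move between control and intervention wards | Split at transfer (Intervention); listed as a censoring reason (Table 3) |
| Before first arrival on an enrolled ward | None; counted from insertion |
| After a move to a non-enrolled area | None; counted to removal, followed to discharge or removal |
| Move between two wards of the same status | None |

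The split in the first row also needs a transfer date, which is not among the listed items.

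**3. Direction of the effect.** Let f be the share of counted catheter-days that are off-ward, and r the true relative reduction in on-ward catheter-days. Take patient-days and off-ward days as unaffected by the tag. Then:

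- reduction seen = r(1 − f)
- inflation of the control-phase ratio, if patient-days are ward-based = 1/(1 − f)

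The assumption about off-ward days is secure for those before arrival. For those after departure it overstates the attenuation, because a catheter removed on the ward before the move adds none.

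**4. Illustrative size.** From the protocol: median duration 4 days. Assumed, since the protocol gives no figures: 25% to 75% of catheters already in place on arrival, with a mean of 0.5 to 2 off-ward days each; an exponential duration; r = 20%.

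- Mean duration = 4/ln 2 = 5.77 days
- Off-ward days per catheter: 0.25 × 0.5 = 0.125, up to 0.75 × 2 = 1.5
- f: 0.125/5.77 = 0.022, up to 1.5/5.77 = 0.26
- Reduction seen: 20% × (1 − 0.022) = 19.6%, down to 20% × (1 − 0.26) = 14.8%
- Inflation if patient-days are ward-based: 5.77/5.645 = 1.02, up to 5.77/4.27 = 1.35

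**5. Sensitivity to the distribution.** Data analysis anticipates normally distributed durations. The mean would then equal the 4-day median, f would run from 0.125/4 = 0.031 to 1.5/4 = 0.375, and the reduction seen from 19.4% to 12.5%.

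**The case against.** The strongest reply is that the counting sentence is a general rule and the transfer paragraphs its exception. Table 3 carries that exception as a censoring reason, so the two can be read together for control/intervention moves. That stands. A reader might infer that days are credited to a ward wherever in the hospital the catheter is finally removed. The text does not support this, because time is cut when the patient moves to a ward of the other status. The three remaining rows of the table in the working are not answered by this reply.

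It is also fair that the statement on varied insertion settings was written to justify a waiver of consent and gives no share. Because the count runs by date, a catheter inserted elsewhere on the day of arrival may add no earlier day. At the low end of the illustration the loss is negligible. These objections limit the size, not the existence, of the gap.

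A reader might take inflation of the ratio as established, or as bias in favour of the tag. Neither follows. The protocol never says where patient-days are counted, and Table 3 does not list them. Each ward also serves as its own control, so stable pre-arrival days raise the ratio in both phases and weaken the contrast; they do not create one.

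Last, insertion-to-removal time suits the duration variable named under Data analysis, and stopping the count at ward departure could make transfers look like shorter catheterisation. That is a real cost, which the fix must handle.

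**Conclusion.** The concern holds in a bounded form. As written, the rule admits catheter-days before first arrival on an enrolled ward and after a move to a non-enrolled area into a ward-randomised ratio, and the listed data items do not allow them to be removed later. The consequence is attenuation, with inflation of the ratio only if patient-days are ward-based.

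The size cannot be computed from the protocol. The 19.6% to 14.8% range rests on an assumed off-ward share, assumed off-ward days and an exponential shape. It borrows 20% as a round figure: the protocol's own 20% is a relative fall in the probability of a catheter in situ on day 4, not in catheter-days. For that reason no loss of the stated 81% power is claimed. A reader might also infer that the secondary outcome on insertions per 100 admissions should be confined to on-ward insertions; nothing examined here establishes that.

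The change should be made before data collection.

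**What to change.** - Reconcile the Intervention section, the Data collection text and Table 3. For the utilisation ratio, count both catheter-days and patient-days only while the patient is on the enrolled ward. Catheter-days then run from the later of insertion and ward arrival to the earliest of removal, ward departure, discharge or study end.
- Apply the same bounds to moves between two wards of the same status, so that each ward receives its own days.
- Add ward arrival and departure or transfer date and time to Table 3.
- Add a move to a non-enrolled area to the reasons for censoring.
- In any analysis of duration, treat ward departure as censoring, not as catheter removal.
- Keep total insertion-to-removal duration as a separate descriptive figure.

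The cost is a few extra fields from medical notes already being read, and some rewording. The price in substance is that total in-hospital catheter time is no longer the quantity counted for the primary outcome.

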#### Sample size:

The at risk population has been defined as patients receiving catheters in hospital. Based on pilot work, an estimated 25% of admissions will receive a catheter. We estimate that, at baseline, the median duration of catheterisation is 4 days (equivalent to a 50% probability that a catheter will be in situ on day 4). We aim to detect a difference of 20% relative risk (10% absolute risk) reduction in catheterisation on day 4, using a stepped wedge study. It is assumed the intra-ward correlation in catheter duration is  $\rho=0.1$ ). Based on pilot work it is anticipated that there will be 50 patients with a catheter per month on each ward and the study will continue for 6 months.

A power calculation was performed using the stepped wedge module in Stata. This accounts for both the clustering in outcomes by ward, as well as the paired/crossover design of the study.

At a significance level of 0.05, 2100 patients (10 wards, with 2 wards implementing the intervention at each month, forming one cluster) will be required to demonstrate a change in the probability of a catheter being in situ on day 4 from 50% to 40% with a power of 81%. Similar power would be expected with 35 patients with catheters per month in 10 wards, with two wards implementing the intervention each month (n=2100, power 81%).

*Objective 2: To determine whether the CATH TAG has an effect on nurses' ability to deliver patient care.*

#### Survey:

Data collection will involve the use of a structured anonymous online survey and focus group. The online survey will be administered using SurveyMonkey. Participants will be asked a series of questions that relate to their perceptions about ease of use of the CATH TAG, their views on effectiveness of the CATH TAG, an exploration of their perceptions of change in ownership or interest by patients in catheter management and any barriers to the CATH TAG working successfully nurses might be experiencing, forming the following four dimensions, based on the objectives of the study:

- Ease of use
- Effectiveness
- Perceived changes in ownership regarding patients' health care
- Barriers

Items, exploring those dimensions, will be presented to participants in the form of statements, to be answered on a 5-point Likert scale, as well as in the form of open questions and yes/no questions to investigate possible themes for the focus-group.

Additionally, demographic information about the participants will be collected, including the ward on which they primarily work, age, sex, years of nursing experience (post qualification) and their highest (completed) qualification. No identifiable or re-identifiable information will be collected.

Focus group:

Participants in the focus group will be limited to approximately six to eight people, to ensure the group can be run effectively. If required, a second focus group might be run to ensure representation from more wards. The focus group will be conducted in a location other than the ward on which the participants work. A person with relevant training and experience will lead the group discussion. An exploration of experiences of the CATH TAG will be undertaken, using a series of questions to prompt discussion. The questions will be designed to validate the broad responses and themes received in the online survey and provide the opportunity for in depth feedback not otherwise possible from the online survey.

The timing of this focus group is important. As this study adopted a stepped wedge cluster approach to implement the intervention, scheduling the focus group towards the end of the study will enable the researchers to capture the participants' responses after staggered levels of involvement in use of the CATH TAG.

Using a phenomenological approach, which seeks to understand the participants' lived experience of a phenomena, the focus group questions will aim to capture information about the personal experiences of the hospital personnel, and their construed perceptions of patients' perceptions, regarding the use and effectiveness of the CATH TAG. Clinical staff will be asked to provide responses to questions about the following issues, including both their own perceptions about use of the CATH TAG as well as their construed perceptions of patients' response to its use:

- perceived ease of use of the CATH TAG;
- perceived impact on patient care (effectiveness) of the CATH TAG;
- perceived impact on interactions with patients as a result of using the CATH TAG;
- perceptions of patients' experiences with, interest in and reactions to use of the CATH TAG;
- perceptions of impact on patients' ownership of their own healthcare as a result of using the CATH TAG;

- perceived barriers to using the CATH TAG; and
- additional issues that emerge from an analysis of the participants' survey responses.

The focus group will be voice recorded, with the permission of participants, to enable further analysis of the discussion at a later day. No identifiable or re-identifiable information provided during the focus group will be linked to any participant.

### ***Data analysis***

*Objective 1: To determine the efficacy of an electronic reminder system in reducing urinary catheter usage.*

The primary outcome measure is the duration of catheterisation, and the study aims to evaluate the effect of the intervention. The analysis will be performed using the generalised estimating equations, using the duration of catheterisation as the dependent variable and intervention as the independent variable. Duration of the intervention will be treated as a confounding variable. It is anticipated that duration of catheterisation will be normally distributed, but exploratory analyses (and where necessary transformation) will be performed. Robust standard errors will be used to adjust for correlation at ward level and autocorrelation in time. There is no expected delay in the effect of the intervention on the outcome.

*Objective 2: To determine whether the CATH TAG has an effect on nurses' ability to deliver patient care.*

Survey:

Data from the anonymous online survey will be analysed using SPSS. It is anticipated that data will be normally distributed but exploratory analyses will be performed, including testing of assumptions of linearity, homoscedasticity, multicollinearity and normality of errors and if necessary transformation of data. Validity and reliability will be examined. Subsequently a general satisfaction score and individual satisfaction scores for the four dimensions of nurses' experiences with the CATH TAG (Ease of use, Effectiveness, Changes in ownership, Barriers) will be calculated. Regression analysis will be conducted to determine if the duration of the intervention or the ward nurses primarily work on had an effect on nurses' experiences with the CATH TAG.

Any problems reported in the open questions will be taken into the focus group to be discussed and subsequently analysed qualitatively (see below).

Focus group:

Data gathered from the focus group/s will be coded and analysed using qualitative analysis software (NVivo). The data analysis process will aim to identify and investigate both, pre-determined and emerging themes, in the data. The pre-determined themes will be drawn from the broad responses to the open questions in the survey, as well as from the study's objectives and will be reflected in the focus group questions. As themes are identified in the data, constant comparison analysis will be utilised. This process reduces redundancy in the analysis results by collapsing similar themes, identifies any relationships between the themes and ensures saturation is achieved. In this way, the essence of the hospital personnel's perceptions will be determined.

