DATA COLLECTION	Data will be collected prospectively on the number of catheters being used during the control and intervention periods.
STATISTICAL ANALYSES	
Objective 1
 
Data analysis will be performed using the generalised estimating equations, with the duration of catheterisation as the dependent variable, and intervention as the independent variable.
 
Objective 2
 
Through an online survey and focus group the data analysis process will aim to investigate pre-determined themes reflected in the study's objectives as well as to identify emerging themes.

DISSEMINATION	The investigators will implement a dissemination plan that will include communication strategies for all stakeholders, a publication plan (to minimally include a protocol paper and primary outcomes papers) and presentations at national and international conferences.

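### Objective 1 has two conflicting primary outcomes, and the utilisation ratio declared in the synopsis and Table 2 has no stated analysis, effect size or power

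*Protocol*

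**What the plan says.** Four parts of the protocol bear on this.

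- **Synopsis (Outcome measures) and Outcomes measures, Table 2.** Both give the primary outcome of Objective 1 as "Urinary catheter device utilization ratio (number of urinary catheter-days divided by the number of patient-days").
- **Data analysis, Objective 1.** This section opens with "The primary outcome measure is the duration of catheterisation". Its one model is a generalised estimating equation "using the duration of catheterisation as the dependent variable and intervention as the independent variable", with the remark "It is anticipated that duration of catheterisation will be normally distributed" and transformation if needed. The synopsis paragraph on statistical analyses agrees: "with the duration of catheterisation as the dependent variable, and intervention as the independent variable".
- **Sample size.** The at-risk population is patients who receive a catheter. The 2100 patients are required to show "a change in the probability of a catheter being in situ on day 4 from 50% to 40% with a power of 81" per cent.
- **Data collection, Table 3.** The rows describe patients who received a catheter and their urine specimens. No row gives ward patient-days.

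Registration is described as pending.

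**The concern.** Two quantities carry the label primary, and they are different estimands. Duration is measured only in patients who have a catheter. The ratio is taken over every patient on the ward, so it also depends on how often catheters are inserted and on how long all patients stay. Either can move while the other does not.

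Two things are at stake. The outcome that the synopsis and Table 2 declare primary has no planned test, effect size or power in this document. And because the protocol supports either label, a report could present whichever result is more favourable as primary and cite the protocol for it. Wards are not blinded, which is a further reason to fix one outcome in advance.

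**Working it through.** **1. The passages side by side**

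| | Utilisation ratio | Duration | In situ on day 4 |
|---|---|---|---|
| Called primary | Synopsis, Table 2 | Data analysis | nowhere |
| Model stated | none | GEE (synopsis, Data analysis) | none |
| Effect size and power | none | none directly | 50% to 40%, 81% |
| Denominator data in Table 3 | no patient-days | not needed | not needed |

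**2. What the 81% refers to**

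Inputs from the Sample size section: 10 wards, two crossing over each month (5 steps, 6 monthly periods), 35 catheterised patients per ward per month (35 × 10 × 6 = 2100), intra-ward correlation 0.1, difference 0.10, significance level 0.05 (two-sided assumed).

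The Hussey–Hughes variance is

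Var = Iσ²(σ² + Tτ²) / [(IU − W)σ² + (U² + ITU − TW − IV)τ²]

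- I = 10, T = 6, U = 30, W = 220, V = 110. So IU − W = 80, and U² + ITU − TW − IV = 900 + 1800 − 1320 − 1100 = 280.
- Total variance 0.45 × 0.55 = 0.2475, so τ² = 0.02475 and σ² = 0.22275/35 = 0.006364.
- Var = 10 × 0.006364 × 0.154864 / (0.50914 + 6.93) = 0.001325, SE = 0.0364.
- Power = Φ(0.10/0.0364 − 1.96) = 78.5%.

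With total variance between 0.25 and 0.24 the result is 78.0% to 79.7%. Reading 0.1 as a coefficient of variation gives 81.3%. The stated 81% is thus roughly reproduced, but only for the day-4 binary quantity.

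**3. What the day-4 target means for duration**

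The protocol gives no standard deviation or shape for duration, so a shape must be assumed.

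- Exponential: the mean is 4/ln 2 = 5.77 days when 50% are in situ at day 4, and 4/(−ln 0.4) = 4.37 days when 40% are. The ratio is 0.756, a fall of 24%.
- Weibull with shape k: the ratio is 0.756^(1/k). The fall is about 29% for k = 0.8, 17% for k = 1.5 and 13% for k = 2.
- Normal, as the protocol anticipates: the mean falls by 0.253 standard deviations (−Φ⁻¹(0.4)). With no standard deviation stated, no percentage follows.

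**4. How far the ratio can part from duration**

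Ratio = (catheters inserted × mean days per catheter) / patient-days. Take the exponential case, hold patient-days fixed and let insertions rise (the size of the rise is an assumption):

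| Rise in insertions | Ratio, relative to control | Fall in ratio | Fall in mean duration |
|---|---|---|---|
| 0% | 0.756 | 24% | 24% |
| 10% | 0.756 × 1.1 = 0.832 | 17% | 24% |
| 20% | 0.756 × 1.2 = 0.908 | 9% | 24% |
| 30% | 0.756 × 1.3 = 0.983 | about 2% | 24% |

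**5. Power for the two outcomes called primary**

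Neither can be computed from the protocol. The same variance formula under assumptions gives:

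- Mean duration, difference 5.77 − 4.37 = 1.41 days (unrounded means), intra-ward correlation 0.1, n = 2100: 99.8% if the standard deviation is 4 days, 89% if 6, 67% if 8.
- Utilisation ratio, 10 wards × 6 months, between-ward SD 0.05, relative fall 20% to 24%, baseline 0.10 to 0.26, residual ward-month SD 0.03 to 0.10: about 7% to over 99%. For example, baseline 0.20, residual SD 0.05 and a 20% fall give SE 0.02205 and power Φ(0.04/0.02205 − 1.96) = 44%.

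The 81% carries over to neither.

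**The case against.** The strongest reply is that the plan is more coherent than it looks. The Sample size section derives the day-4 probability from the median duration and states its correlation for catheter duration, so powering and modelling both concern duration, and the ratio may be no more than a summary label. This stands in part. A reader might infer that there are three primary outcomes. The protocol does not support that: only two quantities are called primary, and day-4 status is a cut of one of them. But a model for duration still does not test the powered contrast, and the ratio is labelled primary in two places.

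A second reply is that a rise in insertions would not go unseen, because insertions per 100 admissions is a secondary outcome. That is true and useful, but it does not say which result is primary.

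Third, the divergence in the table rests on assumptions. A reader might infer that re-inserted catheters are counted as separate durations. The protocol speaks of catheter days for each patient and does not say how a re-insertion is handled. If it were pooled within the patient, re-insertion would lengthen duration too. The outcomes would still separate if more patients were catheterised or if length of stay changed.

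Finally, a statistical analysis plan not seen here could contain a model for the ratio, and Figure 2 on data collection is not available in the text reviewed. A later plan can elaborate a primary analysis, but it does not remove a conflict between two primary labels in the protocol.

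**Conclusion.** The point holds as a direct contradiction within the protocol. The synopsis and Table 2 declare one primary outcome, Data analysis declares another, and the power statement covers a dichotomised form of the second. The declared ratio has no analysis, effect size or power stated here, and Table 3 names no source for its denominator.

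The size is illustrative. A 24% fall in mean duration assumes exponential durations (29% to 13% for Weibull shapes 0.8 to 2). The accompanying fall in the ratio, between 24% and about 2%, further assumes insertions up by 0% to 30% and unchanged patient-days.

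Two stronger inferences are not supported. A reader might conclude that the trial will never test the ratio, or that it abandons a registered outcome. The document shows only that no test is stated here, and registration is still pending. Nor is the 81% shown to be materially wrong for the day-4 quantity: the check gives 78% to 81%.

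**What to change.** Before registration:

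1. Name one primary outcome for Objective 1 consistently in the synopsis (outcomes and analyses), Table 2, Sample size and Data analysis, and make the other a named secondary outcome. Either choice removes the contradiction.
2. If the ratio is kept as in Table 2, analyse ward-by-period catheter-days with patient-days as offset or denominator, with terms for intervention and calendar period and allowance for clustering by ward. Add ward patient-days and their source to Table 3.
3. State in the Sample size section that the 81% refers only to the proportion of catheters in situ on day 4. Give the detectable relative change in the ratio under stated assumptions for its baseline and its ward-period variance, neither of which the protocol now supplies.

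The cost is wording, one routine administrative data item and a re-run power statement. That statement may be less favourable than 81%, so it cannot be promised that the present size is enough for the ratio.
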